6.2. Appendix 2: Treatment Compliance

Treatment compliance will be summarized using the mITT population, excluding inadvertently enrolled participants.

The study protocol provides dosing algorithm for both study treatments. The investigator will calculate algorithm recommended dose based on the participant fasting blood glucose and hypoglycemia occurrence reported in e-diary. If the investigator does not agree with the algorithm recommended dose, the investigator will prescribe another dose for the participant and choose the reason of not following the algorithm recommended doses different from a pre specified list of terms. The number and percentage of investigator prescribed doses different from algorithm recommended doses will be provided to evaluate the adherence to the algorithm dose. The reason for not following the algorithm recommended dose will also be summarized.

The first dose of study treatment is administered by site personnel and the subsequent doses are self-administered. The number and percentage of investigator prescribed doses that are not equal to participant administered dose will be provided.

6.3. Appendix 3: Clinical Trial Registry Analyses

Additional analyses will be performed for the purpose of fulfilling the Clinical Trial Registry (CTR) requirements.

Analyses provided for the CTR requirements include the following:

- Summary of adverse events, provided as a dataset which will be converted to an XML file. Both Serious Adverse Events and "Other" Non-Serious Adverse Events are summarized by treatment group, by MedDRA PT.
- An AE is considered 'Serious' whether or not it is a TEAE.
- An AE is considered in the 'Other' category if it is both a TEAE and is not serious. For each Serious AE and 'Other' AE, for each term and treatment group, the following are provided:
 - the number of participants at risk of an event,
 - the number of participants who experienced each event term, and
 - the number of events experienced.
- For each Serious AE, these additional terms are provided for EudraCT:
 - \circ the total number of occurrences causally related to treatment,
 - the total number of deaths, and
 - the total number of deaths causally related to treatment.
- Consistent with www.ClinicalTrials.gov requirements, 'Other' AEs that occur in fewer than 5% of patients/subjects in every treatment group may be excluded if a 5% threshold is chosen. Allowable thresholds include 0% (all events), 1%, 2%, 3%, 4% and 5%.
- AE reporting is consistent with other document disclosures for example, the CSR, manuscripts, and so forth.
- Demographic table including the following age ranges required by EudraCT: in utero, preterm newborn infants (gestational age <37 weeks), newborns (0-27 days), infants and toddlers (28 days 23 months, children (2-11 years), adolescents (12-27 years), adults (18-64 years), 65-85 years, and 85 years and over.

6.4. Appendix 4: Concomitant Therapy

Concomitant therapy is defined as the therapy that starts, before, on, or after the first day of study treatment but before the last dose date in the treatment period, and continues into the treatment period, that is, either no end date (the therapy is ongoing) or an end date on or after the first day of study treatment.

The number and percentages of participants who take concomitant medication will be summarized by treatment using PTs nested within Anatomical Therapeutic Chemical (ATC) Level. The concomitant medications will be ordered by decreasing frequency of LY3209590 within each ATC level.

6.5. Appendix 5: Protocol Deviations

Important protocol deviations (IPDs) are the deviations from the study protocol that may compromise the data integrity and patients' safety. The IPD category and details of IPD identification are provided in the trial issue management plan.

The number and percentage of participants with any reported IPDs will be summarized by treatment group and IPD category. The IPDs identified by site monitoring and clinical database will be integrated. If the IPD is identified by both methods, only the site monitoring IPD will be presented.

6.6. Appendix 6: Derivation of CGM Variables

Blinded CGM will be worn by participants at the following designated weeks:

- Two weeks in screening/lead-in period with the data download at Week 0 (Visit 3),
- Four weeks after the initiation of study treatment with the data download at Week 4 (Visit 7),
- Four weeks near the end of weekly titration period with the data download at Week 12 (Visit 15),
- Four weeks near the primary endpoint with the data download at Week 26 (Visit 22),
- Four weeks near the end of 1-year treatment with the data download at Week 52 (Visit 30),
- Four weeks near the end of study treatment period with the data download at Week 78 (Visit 37), and
- Four weeks after the end of study treatment period with the data download at Week 83 (Visit 802).

Linear interpolation will be used to impute the missing glucose readings during intervals >7 minutes and ≤ 15 minutes. Missing data will be imputed at a 5-minute interval using the BG value before and the one after the interval.

For example, the BG reading before the interval is 50 mg/dL at time 100 min, and the BG reading after interval is 70 at time 115 min, then the missing records will be imputed as:

- at time 105 min, BG reading=50+5*(70-50)/(115-100)=56.7, and
- at time 110 min, BG reading=50+10*(70-50)/(115-100)=63.3.

Glucose reading intervals >15 minutes will be treated as missing data and not be counted in the length of the analysis periods.

As shown in the table below, all the CGM derivations are based on the data from valid CGM periods of a day and period unless otherwise specified.

Period	Definition	Minimum Valid CGM Time Period for a Session		
Valid CGM Day	\geq 70% of expected values	\geq 3 valid CGM days within a visit defines a valid		
(00:00-23:59)	available (≥202 of 288 values)	CGM visit. A valid CGM session only includes valid		
		CGM visits.		
Valid CGM Nighttime	\geq 70% of expected values	\geq 3 valid CGM Nighttime periods within a visit		
(00:00-05:59)	available (≥50 of 72 values)	defines a valid CGM visit. A valid CGM session for		
		nighttime only includes valid CGM visits.		
Valid CGM Daytime	\geq 70% of expected values	\geq 3 valid CGM Daytime periods within a visit defines		
(06:00-23:59)	available 151 of 216 values)	a valid CGM visit. A valid CGM session for daytime		
		only includes valid CGM visits.		

Abbreviation: CGM = continuous glucose monitoring.

For the primary analysis, CGM data must meet above criteria for the period in order to be included as a valid CGM period. Sensitivity analysis will be done for selected parameters including all available CGM data.

The ambulatory glucose profile during the 24-hour period will be generated with interquartile ranges, at treatment-group level by CGM session, based upon the observed CGM measures.

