6.6.1. Glucose in Target Ranges, Hypoglycemia or Hyperglycemia

The following variables of time in range, hypoglycemia, hyperglycemia during each CGM session will be derived:

- Percentage and Duration (in minutes) of time per day where glucose values are within a hypoglycemic range (defined as <54 mg/dL [3.0 mmol/L]) during the nighttime period (defined as midnight to 0600 hours), the daytime period (defined as 0600 hours to 2400 hours) and a 24-hour period.
- Percentage and Duration (in minutes) of time per day where glucose values are within a hypoglycemic range (defined as <70 mg/dL [3.9 mmol/L] and ≥54 mg/dL [3.0 mmol/L]) during the nighttime period, the daytime period and a 24-hour period.
- Percentage and Duration (in minutes) of time per day where glucose values are within a hypoglycemic range (defined as <70 mg/dL [3.9 mmol/L]) during the nighttime period, the daytime period and a 24-hour period.
- Percentage and Duration (in minutes) of time per day glucose values are within a hyperglycemic range (defined as >180 mg/dL [10.0 mmol/L] and ≤ 250 mg/dL [13.9 mmol/L]) during the nighttime period, the daytime period and a 24-hour period.
- Percentage and Duration (in minutes) of time per day glucose values are within a hyperglycemic range (defined as >250 mg/dL [13.9 mmol/L]) during the nighttime period, the daytime period and a 24-hour period.
- Percentage and Duration (in minutes) of time per day glucose values are within a hyperglycemic range (defined as >180 mg/dL [10.0 mmol/L]) during the nighttime period, the daytime period and a 24-hour period.
- Percentage and Duration (in minutes) of time per day glucose values are within a glycemia range (defined as between 70 mg/dL and 180 mg/dL [3.9 and 10.0 mmol/L]) inclusive during the nighttime period, the daytime period and a 24-hour period.
- Percentage and Duration (in minutes) of time per day glucose values are within a glycemia range (defined as between 70 mg/dL and 140 mg/dL [3.9 and 7.8 mmol/L] inclusive) during the nighttime period, the daytime period and a 24-hour period.

The percentage of time within a glucose range (target, hypoglycemia or hyperglycemia ranges) will be calculated as the number of observations within the specified range divided by the number of observations in the time interval (for example, 24-hour period). The average percentage of time among valid CGM days for the corresponding time interval during each CGM session will be used in the analysis.

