The duration (in minutes) within the glucose range will then be calculated as the average percentage of time within the glucose range times the length of the period (24-hour, 18-hour, and 6-hour, for the periods of 24 hour, daytime or nighttime, respectively).

According to the guidance (Battelino et al. 2019), the following CGM targets of glycemic control will also be derived during a 24-hour period.

• The percentage of time within a normal glycemia range (defined as between 70 mg/dL and 180 mg/dL [3.9 and 10.0 mmol/L] inclusive) >70%.

- The percentage of time within a hypoglycemia range (defined as <70 mg/dL [3.9 mmol/L]) <4%.
- The percentage of time within a hypoglycemia range (defined as <54 mg/dL [3.0 mmol/L]) <1%.
- The percentage of time within a hyperglycemic range (defined as >180 mg/dL [10.0 mmol/L]) <25%.
- The percentage of time within a hyperglycemic range (defined as >250 mg/dL [13.9 mmol/L]) <5%.

In addition, according to the guidance in 2023 (Battelino et al. 2023), 2 composite endpoints will be derived during a 24-hour period:

- >70% time in range 70 -180 mg/dL (3.9 10.0 mmol/L inclusive) and <4% time below range <70 mg/dL (<3.9 mmol/L); and
- >70% time in range 70 -180 mg/dL (3.9 10.0 mmol/L inclusive) and <1% time below range <54 mg/dL (<3.0 mmol/L).

The daily duration (in minutes) of time within a glucose range (defined as <54 mg/dL [3.0 mmol/L]; <70 mg/dL [3.9 mmol/L] and \geq 54 mg/dL [3.0 mmol/L]; <0 mg/dL [3.9 mmol/L]; \geq 70 mg/dL[3.9 mmol/L] and \leq 140 mg/dL [7.8 mmol/L]; \geq 70 mg/dL [3.9 mmol/L] and \leq 180 mg/dL [10.0 mmol/L]; >180 mg/dL[10.0 mmol/L] and \leq 250 mg/dL[13.9 mmol/L]; >250 mg/dL [13.9 mmol/L]) will be merged with the dose administration data to get the summary of daily time in each glucose range since dose administration in the each CGM session in the treatment period. For LY3209590, days relative to dose administration will be derived as 0 (dosing day), and then 1, 2, ..., up to 6 days after most recent dose administration but before the next dose administration. The average daily time in hypoglycemia for the given day (0 to 6) relative to the dose administration among valid CGM days (with at least 70% data per day) during each CGM session will be used in the analysis.

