6.6.2. Hypoglycemic Episode

According to the International Consensus Statement (Battelino et al. 2023), the CGM-determined hypoglycemic episodes for Level 1 or 2 and Level 2 are defined as below:

Hypoglycemia Level	Stating Time	Ending Time	Duration
Level 1 or 2 hypoglycemia	Time of the 1st BG of	Time of the last BG of the	Time of the last
(BG <70 mg/dL	BGs <70 mg/dL for	BGs \geq 70 mg/dL for	BG <70 mg/dL – time of
[3.9 mmol/L])	≥15 consecutive minutes	\geq 15 consecutive minutes	the 1st BG <70 mg/dL
Level 2 hypoglycemia (BG <54 mg/dL [3.0 mmol/L])	Time of the 1st BG of BGs <54 mg/dL for ≥15 consecutive minutes	Time of the last BG of the BGs \geq 54 mg/dL for \geq 15 consecutive minutes	Time of the last BG <54 mg/dL – time of the 1st BG <54 mg/dL
Level 2 hypoglycemia	Time of the 1st BG of	Time of the last BG that	Time of the last
ending with	BGs <54 mg/dL for	ensures the BGs ≥70 mg/dL	BG <70 mg/dL – time of
BG ≥70 mg/dL	≥15 consecutive minutes	for 15 consecutive minutes	the 1st BG <54 mg/dL

Abbreviation: BG = blood glucose (as captured in continuous glucose monitor [CGM]).

Note: Starting time and ending time are regardless of number of BG readings.

If the truncated time interval is >7 and \leq 15 minutes, linear interpolation will be used to impute the missing data at 5-minute intervals as described in Section 6.6.

If the truncated time interval is >15 minutes:

- at any time, which make the starting time undeterminable, then do not count this time interval and no episodes start.
- If it is after an episode started, which makes the ending time undeterminable, then the episode ends at the starting time of the truncation.
- If an episode started and continued until the end of a CGM session, then the episode ends at the end of CGM session.

The average duration, incidence, event rate of the Level 1 or 2 and Level 2 hypoglycemia episodes will be analyzed for each CGM session as planned in Section 4.6.3.1.2. The average duration will be calculated by dividing the sum of the duration of individual episodes during the given CGM session by the number of episodes and used in the analysis. The hypoglycemia event rate (events/participant/year) will be calculated by dividing the number episodes by the number of valid CGM days \times 365.25 days.

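### The CGM hypoglycemia event rate counts a valid day with up to 29.9% of its readings missing as a full day at risk, which conflicts with the SAP's own gap rule

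*SAP*

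**What the plan says.** SAP Section 6.6 (Appendix 6) defines three valid CGM periods, each at 70% of expected readings. The 24-hour row reads "available (≥202 of 288 values", the nighttime row (00:00-05:59) "available (≥50 of 72 values", and the daytime row (06:00-23:59) "available 151 of 216 values". The 24-hour row has no condition on when in the day the readings fall. Gaps over 7 and up to 15 minutes are interpolated at 5-minute steps. For longer gaps the rule is: "Glucose reading intervals >15 minutes will be treated as missing data and not be counted in the length of the analysis periods".

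Section 6.6.2 says that the event rate is "calculated by dividing the number episodes by the number of valid CGM days", annualized by 365.25. It also ends an episode in progress at the point where a gap over 15 minutes starts.

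Section 4.6.3.1.2 describes the same rate as events over days at risk. It uses log exposure in years as the negative binomial offset and refers to Appendix 6 for missing data.

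For time in range, Section 6.6.1 takes in-range readings "divided by the number of observations in the time interval (for example, 24-hour period". It then states: "The average percentage of time among valid CGM days for the corresponding time interval during each CGM session will be used in the analysis". Duration is that percentage "times the length of the period (24-hour, 18-hour, and 6-hour, for the periods of 24 hour, daytime or nighttime, respectively".

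**The concern.** An event rate needs a denominator that measures time under observation. No episode can be seen during a long gap, so counting the gap as time at risk lowers the rate. Section 6.6 appears to exclude such time and Section 6.6.2 appears to include it. A programmer has to choose between them, and the result depends on the choice. Participants, sessions or arms with poorer capture would look safer. The trial is open-label, so equal capture in the two arms cannot be taken for granted.

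A related question concerns the 24-hour summaries. Daytime alone offers 216 readings and only 202 are needed, so a day without any night data can qualify. Time in range before Week 26 is an alpha-controlled key secondary endpoint, and time below 54 mg/dL is a secondary safety endpoint. Under-weighting the night could matter for both.

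**Working it through.** **1. The stated cut-offs.** Inputs are the three rows of the validity table in SAP 6.6.
- 24-hour: 0.70 x 288 = 201.6, rounded up to 202. This reproduces the SAP's figure (202/288 = 70.1%).
- Night: 0.70 x 72 = 50.4, so 51 are needed. The stated 50 gives 69.4%.
- Day: 0.70 x 216 = 151.2, so 152 are needed. A cut-off of at least 151 gives 69.9%. The comparison sign is missing from this cell in the text available, so this row needs confirming only.
- With 51 and 152, a day that passes both parts has at least 203 readings and always passes the 24-hour rule. With 50 and 151 the sum is 201, and it might not.

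**2. How incomplete a valid day may be.** 288 - 202 = 86 readings, which is 86/288 = 29.9%, or 86 x 5/60 = about 7.2 hours.

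**3. Effect on the event rate.** Let c be the completeness within valid days (observed plus interpolated readings / 288). The day-count rate is episodes / days. The observed-time rate is episodes / (days x c). If events are uniform over the day, the day-count rate is c times the observed-time rate.

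| Completeness c | Understatement (1 - c) | Observed-time / day-count rate |
|---|---|---|
| 0.95 | 5% | 1.05 |
| 0.90 | 10% | 1.11 |
| 0.75 (no night readings) | 25% | 1.33 |
| 0.701 (limit) | 29.9% | 1.43 |

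**4. Effect on the rate ratio.** The multiplier is c in the LY3209590 arm divided by c in the degludec arm. Equal capture (0.95 and 0.95) gives 1.00. Assumed capture of 0.90 against 0.95 gives 0.947, and 0.80 against 0.95 gives 0.842.

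**5. If events are not uniform.** Suppose every night is missing and a share q of events falls at night. The day-count rate is then (1 - q) times the true rate, and the observed-time rate is (1 - q)/0.75 times the true rate. For assumed q of 0.10, 0.25 and 0.40:
- day-count: 0.90, 0.75 and 0.60
- observed-time: 1.20, 1.00 and 0.80

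Observed time corrects the exposure. It cannot supply the missing nights.

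**6. Night coverage and 24-hour time in range.** 216 is at least 202, with 14 to spare, so a day with 0 of 72 night readings is valid. Its percentage is a daytime percentage. True 24-hour time in range is 0.75 x day + 0.25 x night, so that day's error is 0.25 x D, where D is day minus night. An assumed D of 10 to 20 points gives 2.5 to 5 points for that one day.

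If a share s of days lacks the night in both arms, the arm difference moves by s x 0.25 x (arm difference in D). Two assumed cases:
- s = 10% and 5 points: 0.10 x 0.25 x 5 = 0.13 points
- s = 20% and 10 points: 0.20 x 0.25 x 10 = 0.5 points

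From the planning values in SAP Section 5, the standard error of the arm difference is 18 x sqrt(1/532 + 1/266) = 1.35 points.

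**The case against.** The strongest reply on the rate is that Section 4.6.3.1.2 sends missing-data handling to Appendix 6. The modeled exposure could then already leave out long gaps, which would make this an unclear text and not an established understatement. That stands in part: the offset is undefined, not demonstrably wrong. But Section 6.6.2 is also in Appendix 6 and gives an explicit formula with whole days, so the reference does not resolve the conflict.

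It also stands that an episode cut at a gap may be counted again if low glucose continues afterwards, which partly offsets the understatement. The 30% figure needs every valid day to sit at the limit. CGM event rates are not in the objectives table, and the alpha-controlled nocturnal hypoglycemia endpoint is participant-reported.

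A reader might infer more about time in range, and the documents do not support it:
- Time in range does not breach the gap rule, because its denominator is the readings in the interval.
- A participant's session value is daytime-only only if every valid day lacks night data. Each such day would need 202 of 216 daytime readings (93.5%). No document shows that pattern occurring.
- The 2.5 to 5 points is an error in one day under an assumed day-night gap. It should not be set against the planned 5-point difference between arms.
- Nocturnal lows are not hidden, because night metrics are derived separately with their own validity rule.

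The SAP also plans 24-hour glucose profiles, missing-data summaries by day, visit and session, and an all-available-data sensitivity analysis for selected parameters. The protocol adds an 80% session compliance threshold. These help, but none requires night coverage or changes the rate denominator.

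**Conclusion.** The rate denominator in Section 6.6.2 and the gap rule in Section 6.6 conflict, and Section 4.6.3.1.2 leaves the offset unreconciled. With uniform event risk, and before any offset from split episodes, CGM rates are understated by one minus completeness within valid days: 5% at 95% capture and at most about 30%. The treatment comparison is biased only if capture differs by arm, and the documents give no capture data. The nighttime cut-off is one reading short of the stated 70%; the daytime cut-off needs confirming.

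The lack of a night condition on the 24-hour day is real but of unknown consequence. It can under-weight the night in time in range and time below 54 mg/dL. How often it occurs, the direction of any bias in time in range and any effect on the arm difference are not shown. It does not justify changing the primary day definition.

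**What to change.** In SAP Appendix 6 and Section 4.6.3.1.2:

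1. Define exposure for CGM event rates, and for the model offset, as observed plus interpolated CGM time within valid days: readings x 5 / 1440 days. State how an episode interrupted by a gap over 15 minutes is counted when low glucose continues after it.
2. Correct the nighttime cut-off to at least 51 of 72, and confirm that the daytime cut-off is at least 152 of 216.
3. Keep the primary 24-hour day definition. Add a sensitivity analysis of Week 26 time in range and time below 54 mg/dL, limited to days that also meet the Daytime and Nighttime criteria.

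The cost is a small derivation change and one extra analysis using validity flags that the SAP already defines. Day-and-night validity is better as a sensitivity analysis than as the primary rule because it drops fairly complete days. With the corrected cut-off, a day with all 216 daytime and 50 night readings (266/288 = 92.4%) would go. Some visits could then fall below three valid days, which would send more participants to imputation. The SAP version history also records that the definitions of valid CGM periods and visits were clarified on FDA advice. If the database is already locked, the observed-time rate can be reported as a labeled sensitivity analysis.

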6.6.1. Glucose in Target Ranges, Hypoglycemia or Hyperglycemia

The following variables of time in range, hypoglycemia, hyperglycemia during each CGM session will be derived:

- Percentage and Duration (in minutes) of time per day where glucose values are within a hypoglycemic range (defined as <54 mg/dL [3.0 mmol/L]) during the nighttime period (defined as midnight to 0600 hours), the daytime period (defined as 0600 hours to 2400 hours) and a 24-hour period.
- Percentage and Duration (in minutes) of time per day where glucose values are within a hypoglycemic range (defined as <70 mg/dL [3.9 mmol/L] and ≥54 mg/dL [3.0 mmol/L]) during the nighttime period, the daytime period and a 24-hour period.
- Percentage and Duration (in minutes) of time per day where glucose values are within a hypoglycemic range (defined as <70 mg/dL [3.9 mmol/L]) during the nighttime period, the daytime period and a 24-hour period.
- Percentage and Duration (in minutes) of time per day glucose values are within a hyperglycemic range (defined as >180 mg/dL [10.0 mmol/L] and ≤ 250 mg/dL [13.9 mmol/L]) during the nighttime period, the daytime period and a 24-hour period.
- Percentage and Duration (in minutes) of time per day glucose values are within a hyperglycemic range (defined as >250 mg/dL [13.9 mmol/L]) during the nighttime period, the daytime period and a 24-hour period.
- Percentage and Duration (in minutes) of time per day glucose values are within a hyperglycemic range (defined as >180 mg/dL [10.0 mmol/L]) during the nighttime period, the daytime period and a 24-hour period.
- Percentage and Duration (in minutes) of time per day glucose values are within a glycemia range (defined as between 70 mg/dL and 180 mg/dL [3.9 and 10.0 mmol/L]) inclusive during the nighttime period, the daytime period and a 24-hour period.
- Percentage and Duration (in minutes) of time per day glucose values are within a glycemia range (defined as between 70 mg/dL and 140 mg/dL [3.9 and 7.8 mmol/L] inclusive) during the nighttime period, the daytime period and a 24-hour period.

The percentage of time within a glucose range (target, hypoglycemia or hyperglycemia ranges) will be calculated as the number of observations within the specified range divided by the number of observations in the time interval (for example, 24-hour period). The average percentage of time among valid CGM days for the corresponding time interval during each CGM session will be used in the analysis.

The duration (in minutes) within the glucose range will then be calculated as the average percentage of time within the glucose range times the length of the period (24-hour, 18-hour, and 6-hour, for the periods of 24 hour, daytime or nighttime, respectively).

According to the guidance (Battelino et al. 2019), the following CGM targets of glycemic control will also be derived during a 24-hour period.

• The percentage of time within a normal glycemia range (defined as between 70 mg/dL and 180 mg/dL [3.9 and 10.0 mmol/L] inclusive) >70%.

- The percentage of time within a hypoglycemia range (defined as <70 mg/dL [3.9 mmol/L]) <4%.
- The percentage of time within a hypoglycemia range (defined as <54 mg/dL [3.0 mmol/L]) <1%.
- The percentage of time within a hyperglycemic range (defined as >180 mg/dL [10.0 mmol/L]) <25%.
- The percentage of time within a hyperglycemic range (defined as >250 mg/dL [13.9 mmol/L]) <5%.

In addition, according to the guidance in 2023 (Battelino et al. 2023), 2 composite endpoints will be derived during a 24-hour period:

- >70% time in range 70 -180 mg/dL (3.9 10.0 mmol/L inclusive) and <4% time below range <70 mg/dL (<3.9 mmol/L); and
- >70% time in range 70 -180 mg/dL (3.9 10.0 mmol/L inclusive) and <1% time below range <54 mg/dL (<3.0 mmol/L).

The daily duration (in minutes) of time within a glucose range (defined as <54 mg/dL [3.0 mmol/L]; <70 mg/dL [3.9 mmol/L] and \geq 54 mg/dL [3.0 mmol/L]; <0 mg/dL [3.9 mmol/L]; \geq 70 mg/dL[3.9 mmol/L] and \leq 140 mg/dL [7.8 mmol/L]; \geq 70 mg/dL [3.9 mmol/L] and \leq 180 mg/dL [10.0 mmol/L]; >180 mg/dL[10.0 mmol/L] and \leq 250 mg/dL[13.9 mmol/L]; >250 mg/dL [13.9 mmol/L]) will be merged with the dose administration data to get the summary of daily time in each glucose range since dose administration in the each CGM session in the treatment period. For LY3209590, days relative to dose administration will be derived as 0 (dosing day), and then 1, 2, ..., up to 6 days after most recent dose administration but before the next dose administration. The average daily time in hypoglycemia for the given day (0 to 6) relative to the dose administration among valid CGM days (with at least 70% data per day) during each CGM session will be used in the analysis.

